4.1.3. Secondary endpoints

a. Assessment of the diagnostic accuracy of “In-Clinic LVAT” test at M0 follow-up: Independent reviewer validation of LV threshold value provided by algorithm

This endpoint is the number of accurate determination of the pacing threshold value provided by the algorithm feature and an independent reviewer, on all LV pacing vectors and all pacing configurations available at M0 follow-up.

Diagnostic accuracy is defined as an adjudication of LV threshold value provided by the algorithm. The adjudication is based on capture and loss of capture analysis on electrogram strips recorded and stored during “In-Clinic LVAT” tests. The threshold value provided by the algorithm compared to the reviewer adjudication is considered accurate if the difference is within ± 1 step. The reason for incorrect determination of capture/loss of capture (if any) will be reported.

In case several LV Vector Tests were eligible with the same LV pacing vector, in the same pacing configuration, for the same subject, on the same follow-up, only the last one will be considered.

b. Assessment of the success rate of “In-Clinic LVAT” test at M0 follow-up: comparison to manual LV threshold tests results

This endpoint is the success rate of “In-Clinic LVAT” feature on pacing vectors and pacing configurations available at M0 follow-up. The method of analysis is similar to the primary endpoint.

c. Assessment of the success rate of “In-Clinic LVAT” test at M1 follow-up: comparison to manual LV threshold tests results

This endpoint is the success rate of “In-Clinic LVAT” feature on pacing vectors and pacing configurations available at M1 follow-up. The method of analysis is similar to the primary endpoint.

d. Evaluation of the applicability of the algorithm

The algorithm may not be applicable to some subjects, mainly because of a very long inter-ventricular conduction delay. A subject is defined as eligible as soon as one LV Vector Test is complete.

The endpoints for the applicability of the algorithm in the population are:

- The percentage of subjects who are eligible to receive the feature that is the percentage of subjects with at least one complete LV Vector Test at M0 and M1 follow-ups.
- The number of LV Vector Tests attempted, and percentage of completed and successful LV Vector Tests at M0 and M1 follow-ups per subject.

e. Assess the device characteristics in terms of safety and deficiencies

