8.2. ANALYSIS POPULATION

The analysis populations will be reviewed and determined during the Data Review meeting based on all included subjects. The included population will consist of all subjects who have completed "Inclusion Form".

The main analysis populations are:

- The Intention To Treat (ITT) population will consist of all included subjects with at least 1 eligible complete LV Vector Tests at M0 follow-up (if unavailable, M1 follow-up will be considered). This population will be used for the assessment of the primary endpoint (see section 4.1.2).
- The M0-Intention To Treat (M0-ITT) population will consist of all included subjects with at least 1 eligible complete LV Vector Tests at M0 follow-up. This population will be used for the assessment of the secondary endpoints concerning the LV test done at M0 follow-up (see section 4.1.3).
- The M1-Intention To Treat (M1-ITT) population will consist of all included subjects with at least 1 eligible complete LV Vector Tests at M1 follow-up. This population will be used for the assessment of the secondary endpoints concerning the LV test done at M1 follow-up (see section 4.1.3).
- The included population will be used for the assessment of the secondary endpoint “Applicability of the algorithm” (see section 4.1.3).
- The safety population will consist of all subjects included and implanted with Platinium SonR CRT-D 1811, 1841 or 1844. The number of subjects in each population will be mentioned in the disposition of subjects.
- Ancillary population will consist of all included subjects with at least one right ventricular pacing electrogram collected during RV A-test or RV P-test at M0 or/and M1 follow-up (see section 4.1.4).

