3. DOCUMENT AND CHANGE HISTORY

3.1. CHANGES IN ANALYSIS COMPARED TO PROTOCOL

Not applicable.

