6.2. EVALUABLE POPULATION (EP)

The evaluable population will consist of IP excluding the subjects having a protocol deviation on “Eligibility Criteria: Right atrial, right and left ventricles lead must be implanted. Only Bipolar or quadripolar for left ventricular lead”. A subject whose termination date occurred prior to M0 visit, will be excluded from this population.

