10.4. EVALUATION OF THE APPLICABILITY OF THE ALGORITHM

The algorithm may not be applicable to some subjects, mainly because of a very long inter-ventricular conduction delay (VV delay). A subject is defined as “eligible” if he/she has at least one complete LV vector test in either of the M0 or M1 visit.

The endpoints for the applicability of the algorithm in the population are:

- A. The number and percentage of subjects who are “eligible” to receive the algorithm. Percentage will be calculated based on the total number of subjects included in the EP, that is:

Number of subjects with at least one complete LV Vector Test at M0 or M1 visits/ Total Number of subjects in EP.

- B. For subject having IS1 lead, up to 6 LV vector tests over 3 LV pacing configurations will be attempted for each subject at each visit.

Among all the subjects having IS1 leads, the number and percentage of subjects having no, one, two,..., six Attempted, Completed and Successful LV vector tests will be presented by LV pacing configuration and visit.

Among all the subjects having IS4 leads, the number and percentage of subjects having one, two,..., fourteen Attempted, Completed and Successful LV vector tests will be presented by LV pacing configuration and visit.

Only subjects with non-missing manual data will be considered.

Percentages calculated based on the number of subjects in EP with the respective lead and configuration will be presented for Attempted, Completed and Successful LV tests.

This information will also be presented with the help of histograms.

This analysis will be based on EP.

This will also be listed.

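### SAP 10.4 A moves the applicability endpoint from the protocol's included population to the smaller EP, while SAP 3.1 declares no change from the protocol

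*SAP*

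**What the plan says.** Protocol 8.2 names the population for applicability: "The included population will be used for the assessment of the secondary endpoint" on applicability of the algorithm. It defines that set broadly: "The included population will consist of all subjects who have completed" the inclusion form. Protocol 8.2 has no evaluable population.

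SAP 10.4 A uses a different base: "Percentage will be calculated based on the total number of subjects included in the EP". It gives the ratio as "Number of subjects with at least one complete LV Vector Test at M0 or M1 visits/ Total Number of subjects in EP", and 10.4 closes by placing the analysis on EP. SAP 6.2 builds EP with two exclusions. The first concerns leads: "The evaluable population will consist of IP excluding the subjects having a protocol deviation on" the lead eligibility criterion. The second concerns timing: "A subject whose termination date occurred prior to M0 visit, will be excluded from this population".

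Protocol section 8 requires a relevant major change to the analysis to be made by protocol amendment or listed in a dedicated SAP section with its rationale. SAP 3.1 is that section, and its whole content is "Not applicable". The change history in SAP 3.2 lists 10.4 among the updated sections, but the changes it describes concern non-missing manual values, table percentages, wording and clarifications. They do not concern the population.

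**The concern.** The denominator of a named secondary endpoint differs between protocol and SAP, and the section meant to record such differences is empty. The exclusions are also not neutral for this endpoint. Applicability is the share of subjects with at least one complete LV Vector Test. Someone who leaves before M0 has no such test, so that person counts as not eligible under the protocol and disappears under the SAP.

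At stake is how the reported percentage will be read. A reader with the protocol in hand would take it as the share of all included subjects, when it is the share of a selected set. If anyone is excluded, the two figures will usually differ, and nothing in the plan warns the reader.

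**Working it through.** **Inputs**
- Planned enrolment N = 59: 47 evaluable subjects and 20% attrition, so 47/(1 − 0.20) = 58.75, rounded up to 59 (Protocol 8.1, SAP 2.3). This reproduces the plan's figure.
- The gap is 59 − 47 = 12 subjects. Both the protocol and the SAP apply the 20% to the study as a whole, not to the period before M0.
- The documents state neither an expected applicability rate nor a number excluded from EP. Both are varied below as assumptions.

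**Formulas.** Let d be the number excluded from EP, x the EP subjects with at least one complete test, and c the excluded subjects with at least one complete test.
- SAP figure: x/(N − d)
- Protocol figure: (x + c)/N

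The SAP figure is larger exactly when x/(N − d) > c/d, that is, when the rate inside EP exceeds the rate among the excluded.

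**Direction**
- Terminated before M0: LVAT tests are scheduled only at M0 and M1, so c = 0. Removing these subjects raises the percentage whenever x > 0.
- Lead deviation: c can be above zero. A subject without an atrial lead, for instance, might still complete a test in VVI, which is a study configuration (SAP 5.6). If one such subject is the only exclusion and 56 of 59 are eligible, 56/59 = 94.9% becomes 55/58 = 94.8%, a small fall.

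**Size, with c = 0 and N = 59**

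| Excluded d | EP size | All EP eligible: IP vs EP | About 95% of EP eligible: IP vs EP |
|---|---|---|---|
| 0 | 59 | 59/59 = 100% vs 100% | 56/59 = 94.9% vs 94.9% |
| 1 | 58 | 58/59 = 98.3% vs 100% | 55/59 = 93.2% vs 55/58 = 94.8% |
| 3 | 56 | 56/59 = 94.9% vs 100% | 53/59 = 89.8% vs 53/56 = 94.6% |
| 6 | 53 | 53/59 = 89.8% vs 100% | 50/59 = 84.7% vs 50/53 = 94.3% |
| 12 | 47 | 47/59 = 79.7% vs 100% | 45/59 = 76.3% vs 45/47 = 95.7% |

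The last row puts the whole 20% attrition before M0 and is an upper bound under the planned attrition. M0 falls within 15 days of inclusion, while M1 follows M0 by one to three months, and losses after M0 do not remove a subject from EP.

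**Is the protocol figure available elsewhere?** SAP 6.3 defines ITT as EP subjects with at least one eligible complete test at M0 or M1, and SAP 7.1 tabulates ITT as a percentage of IP. That ratio is x/N. It differs from the protocol figure only by c and by any distinction between an eligible complete test and a complete test. It is nearly the same number, but it is not labelled as applicability.

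**The case against.** The best defence is that EP suits the question. Both documents treat applicability as a property of the algorithm, limited mainly by a long inter-ventricular conduction delay. A subject who withdrew before any test says nothing about that, and counting such a subject as not applicable mixes attrition into the rate. This stands as a reason to show the EP percentage. It does not excuse leaving the change undeclared when the protocol names another population.

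A second defence is that the disposition table in SAP 7.1 nearly gives the protocol figure and reports discontinuations before M0 with reasons. That lowers the stakes, but a reader would have to find the number and recognise it.

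Third, the declaration rule covers relevant major changes, and whether a denominator change for a descriptive endpoint is major is a judgement. Protocol 8.2 also leaves populations to be determined at the data review meeting. Neither point cancels its explicit assignment of this endpoint to the included population.

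Stronger readings are tempting, but the documents do not support them:
- **The percentage can only rise.** This holds for subjects terminated before M0, but not for a lead-deviation subject with a complete test.
- **The gap will be about 20 points.** That needs the whole study-wide attrition to fall before M0, and no pre-M0 loss rate is given.
- **EP was chosen to improve the result.** SAP 3.2 dates the initial release 19 Feb 2018, and the dataset named in SAP 17.8 carries 20180112 in its file name. Neither shows that anyone looked at applicability before choosing EP.

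**Conclusion.** Wrong as written, with minor severity. The protocol and SAP prescribe different denominators for the same secondary endpoint, and SAP 3.1 incorrectly reports no change. The shift is expected to be upward but is not guaranteed. Its size rests on the unknown number excluded, on few or none of those excluded having a complete test, and on enrolment of 59. With every EP subject eligible, the gap is 0 points for no exclusions, 1.7 for one, 5.1 for three and at most 20.3 for twelve.

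The endpoint is descriptive and has no performance goal. The primary test counts vector tests and does not use this denominator, so this point does not call the primary conclusion into question.

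A related wording difference should be settled in the same edit. Protocol 4.1.3 d describes "the percentage of subjects with at least one complete LV Vector Test at M0 and M1 follow-ups", whereas the SAP ratio counts a test at either visit. The protocol also calls a subject eligible as soon as one test is complete, which is compatible with the SAP's reading, so this is an ambiguity to clear up and not a second demonstrated change.

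**What to change.** 1. In SAP 10.4 A, report applicability on the included population as Protocol 8.2 states. Count the numerator in IP too, so that a complete test from a lead-deviation subject is not lost.
2. Show the EP percentage beside it, labelled as supportive, with the number excluded for each reason. Add a note that ITT as a percentage of IP in SAP 7.1 is nearly the same figure.
3. Replace the content of SAP 3.1 with an entry that names EP, gives the rationale and lists its uses. Besides 10.4 A and B, these include the ITT definition in 6.3 (which Protocol 8.2 draws from all included subjects), the per-protocol set in 6.7, and the analyses in 8.2, 10.1 to 10.3, 11.1 B and C, 13.3, 13.4 and 13.6.
4. State in 10.4 A whether the numerator needs a complete test at either visit or at both.

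The cost is one table column and a short entry in SAP 3.1. No new data are needed and the primary test is unaffected. The only consequence for the sponsor is that the protocol's percentage is likely to be the less favourable of the two.

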For number of LV vector tests “completed”, the percentage will be calculated based on the number of LV vector tests attempted and for number of LV vector tests “accurate”, the percentage calculated based on number of Complete LV vector tests .

A heat plot will be presented for Attempted, Completed and Accurate percentages. If the percentage is > 90%, it will be coloured green, if the percentage is between 75% and 90% (inclusive), it will be coloured brown and if the percentage <75%, then it will be coloured orange.

This will also be listed.

For this analysis, EP will be used considering M0 visit only.

10.2. ASSESSMENT OF THE SUCCESS RATE OF “IN-CLINIC LVAT” TEST AT M0 VISIT: COMPARISON TO MANUAL LV THRESHOLD TESTS RESULTS

This endpoint is the success rate of “In-Clinic LVAT” feature on LV pacing vectors and LV pacing configurations available at M0 visit.

The threshold obtained from the “In-Clinic LVAT” feature, extracted from RTD files, will be compared against manual LV threshold values recorded in the eCRF. The definition of equivalence is same as that of primary analysis.

Test will be evaluated at different LV pacing configuration: DDD A-test, DDD P-test and VVI test. Among all the eligible complete LV Vector Tests collected, only those with a manual LV threshold test performed in the same conditions (same pacing pulse width) at M0 visit and reported in the electronic Case Report Form (eCRF) will be retained.

All analyses performed for this Secondary endpoint will be performed based on manual LV threshold tests results considering data only from M0 visit (except for testing of hypothesis and missing data imputation).

This Secondary endpoint will be based on M0-ITT population.

Decomposition of “In-Clinic LVAT” Success Rate by LV Vector and by LV pacing configuration at M0 visit

Only subjects with non-missing manual data will be considered.

Total number of attempted, completed and successful LV vector tests will be presented by LV vector for each LV pacing configuration.

For number of LV vector tests “attempted”, the percentage will be calculated based on the EP population.

For number of LV tests “completed”, the percentage will be calculated based on the number of LV vector tests attempted.

For number of LV vector tests “Successful”, the percentage will be calculated based on number of Complete LV vector tests.

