A heat plot will be presented for Attempted, Complete and Success percentages. If the percentage is > 90%, it will be coloured green, if the percentage is between 75% and 90% (inclusive), it will be coloured brown and if the percentage <75%, then it will be coloured orange.

For this analysis, EP will be used considering M0 visit only.

10.3. ASSESSMENT OF THE SUCCESS RATE OF “IN-CLINIC LVAT” TEST AT M1 VISIT: COMPARISON TO MANUAL LV THRESHOLD TESTS RESULTS

This endpoint is the success rate of “In-Clinic LVAT” feature on LV pacing vectors and LV pacing configurations available at M1 visit.

The analysis performed for this objective will be exactly similar to that performed for Secondary Objective # 2, but for M1-visit.

For this analysis, M1-ITT population will be used.

LEVEA – Statistical Analysis Plan

For the Decomposition analysis, EP will be used considering M1 visit only.

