A heat plot will be presented for Attempted, Complete, Underestimated percentages. If the percentage is > 90%, it will be coloured green, if the percentage is between 75% and 90% (inclusive), it will be coloured brown and if the percentage <75%, then it will be coloured orange.

This Secondary endpoint will be based on EP population and will also be listed.

C. Analysis of Unexpected Function Operations

Number and percentage of unexpected function operations by analyzing EGM collected in the RTD files and ECG (from DDD A-test) performed during “In-Clinic LVAT” test at each visit will be presented.

- i. Number and percentage of LV vector tests with unexpected functions based on all LV vector tests attempted.
- ii. Number and percentage of LV vector tests with unexpected functions per LV vector per LV pacing configuration per visit

Total number of attempted, completed, with expected function, with unexpected function LV vector tests will be presented by LV vector for each LV pacing configuration by visit.

For the LV tests performed for subjects with either IS1 and IS4 leads six LV vectors common to IS1 and IS4), the percentage for the number of LV vector tests

LEVEA – Statistical Analysis Plan

“attempted”, will be calculated based on the number of subjects implanted with either IS1 and IS4 leads.

For the LV tests performed for patients with IS4 leads (eight LV vectors pertaining only to IS4), the percentage for the number of LV vector tests “attempted”, will be calculated based on the number of patients implanted with IS4 lead.

For number of LV vector tests “completed”, “with Unexpected Function” and “with Expected Function”, the percentage will be calculated based on the number of LV vector tests attempted .

The reasons for unexpected assessment at M0 visit, M1 visit and overall will be presented as table and listing. The missing reasons (if any) for unexpected assessment will be presented as “Not available”. For the table, the number and percentages of the reasons will be presented with the denominator of the percentages based on the total number of unexpected assessments.

All unexpected function operations will be listed.

This Secondary endpoint will be based on EP population.

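### SAP 10.4 B keeps subjects with no M1 visit in the denominator of all three M1 percentages, and 10.3 and 11.1 B and C do so for the attempted percentage, so loss after M0 lowers these descriptive figures

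*SAP*

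**What the plan says.** **Applicability table (SAP 10.4 B).** For IS1 leads, "the number and percentage of subjects having no, one, two,..., six Attempted, Completed and Successful LV vector tests will be presented", split by pacing configuration and by visit. The IS4 table has the same layout but runs from one to fourteen, with no zero row. The denominator for all three quantities is stated once: "Percentages calculated based on the number of subjects in EP with the respective lead and configuration will be presented for Attempted, Completed and Successful" tests. The sentence before the denominator rule reads: "Only subjects with non-missing manual data will be considered".

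**Population (SAP 6.2).** EP is the included population less subjects with a lead-eligibility deviation. For early termination the only rule is: "A subject whose termination date occurred prior to M0 visit, will be excluded from this population". Nothing removes a subject who leaves, or misses the visit, between M0 and M1.

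**M1 decomposition (SAP 10.3).** It repeats 10.2 on M1 data: "For the Decomposition analysis, EP will be used considering M1 visit only". In 10.2 the rule for attempted tests is: "For number of LV vector tests “attempted”, the percentage will be calculated based on the EP population". Completed tests are divided by attempted tests, and successful tests by complete tests.

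**Underestimation and unexpected function (SAP 11.1 B and C).** Both are shown by visit. For vectors common to both leads, the attempted percentage in 11.1 C "will be calculated based on the number of subjects implanted with either IS1 and IS4 leads"; 11.1 B has the same rule. All other percentages in these two tables are divided by attempted or complete tests.

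**Headline rate (SAP 10.4 A).** It is defined as "Number of subjects with at least one complete LV Vector Test at M0 or M1 visits/ Total Number of subjects in EP".

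**The concern.** A subject who is not seen at M1 cannot have a test launched, completed or successful at M1. That absence carries no information about the algorithm. If the subject nevertheless counts in the M1 denominator, attrition is added to non-applicability, and the 10.4 B table, which puts M0 and M1 side by side, can show a fall that the feature did not cause. In the IS1 table such a subject can also land in the zero row, next to subjects in whom the test was tried and failed. In the IS4 table, which has no zero row, the M1 rows would simply add up to less than 100%.

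Protocol 4.1.3 d describes this endpoint as a number of tests attempted and a percentage of tests completed and successful. A percentage of tests is not diluted by absent subjects; the SAP's subject-based denominator is. SAP 5.3 already defines, for each visit, the subjects still in the study at the start of its window, but 10.3, 10.4 and 11.1 do not use that set.

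**Working it through.** **Inputs**
- 47 evaluable subjects, 59 enrolled, 20% attrition in total (SAP 2.3). The split before and after M0 is not given.
- Heat-plot bands: green above 90%, brown from 75% to 90%, orange below 75% (SAP 10.2, applied to M1 through 10.3; the same bands are in 11.1 B).
- Assumptions: 59 included, none removed from EP for a lead deviation, 12 lost in total, 47 attend M1, and every attender has the vector attempted.

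**Step 1: the plan's own figure.** An exact one-sided binomial test of 90% against 95% with n = 231 rejects at 217 or more successes, with alpha 0.0239 and power 81.6%. Then 231/5 = 46.2, rounded up to 47, and 47/(1 − 0.2) = 58.75, rounded up to 59. The sample size reproduces, and the present point does not touch it.

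**Step 2: which M1 percentages have a subject denominator**

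| Table | Attempted | Completed | Other |
|---|---|---|---|
| 10.4 B | EP by lead and configuration | same | Successful: same |
| 10.3 decomposition | EP | attempted tests | Successful: complete tests |
| 11.1 B | implanted subjects | attempted tests | Underestimated: complete tests |
| 11.1 C | implanted subjects | attempted tests | Expected and unexpected function: attempted tests |

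Only the entries based on EP or implanted subjects can move with drop-out.

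**Step 3: ceiling on those entries.** Ceiling = M1 attenders / EP, with EP = 59 − (losses before M0).

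| Lost before M0 | Lost after M0 | EP | Ceiling at M1 |
|---|---|---|---|
| 0 | 12 | 59 | 47/59 = 79.7% |
| 3 | 9 | 56 | 47/56 = 83.9% |
| 6 | 6 | 53 | 47/53 = 88.7% |
| 9 | 3 | 50 | 47/50 = 94.0% |
| 12 | 0 | 47 | 47/47 = 100% |

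With M1 attenders as the denominator, the figure is 100% in every row. The table applies to vectors common to both leads. In 10.4 B the denominators are lead-specific, and the same ratios hold within a lead if losses are proportional.

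**Step 4: completed and successful in 10.4 B.** These shrink by the same factor. As an illustration, if 89% of attenders had a completed test (assumed), the first row of the table would show 0.89 × 47/59 = 70.9%.

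**Step 5: heat-plot colour for attempted cells in 10.3.** With EP = 59, green needs more than 0.90 × 59 = 53.1 subjects, so at least 54. Five subjects without an M1 visit still allow 54/59 = 91.5%; six give 53/59 = 89.8%, which is brown even if every attender is tested.

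**The case against.** **The manual-data sentence may already solve this.** Manual tests are done at each visit and the 10.4 B table is by visit, so a subject with no M1 visit has no M1 manual data and could be read as not considered at M1. Mention of the configuration in the denominator rule also hints at a cell-specific count. This reading is possible, but not secure. The next sentence names EP subjects as the denominator. The change history in SAP 3.2, which lists 10.4 among the updated sections, explains the restriction as a filter on tests, and 11.1 C has no such sentence. The default in SAP 17.2, to divide by subjects with information, applies only where nothing else is defined.

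**A reader might infer that drop-out depresses completed and successful rates throughout the M1 tables, or that no M1 heat-plot cell could be green.** The documents do not support either. Outside 10.4 B those rates are divided by tests. Only attempted cells are capped, and attempted records whether a test was launched, not how the algorithm performed. Neither 10.4 B nor 11.1 C specifies a heat plot.

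**A reader might also infer that the headline applicability rate falls.** It does not fall in this way: 10.4 A accepts a complete test at either visit, so a subject with a complete M0 test still counts after leaving.

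**The 20% attrition may not describe loss after M0.** It inflates 47 evaluable subjects to 59 for the primary analysis, for which M0 data suffice. This stands: 79.7% is the extreme end of a range, not an expectation.

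**Attrition is reported elsewhere.** SAP 7.1 gives visit completion and discontinuations between visits, and SAP 5.3 gives eligible and compliant numbers. A careful reader could untangle the two effects, but the affected tables would still mix them.

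**Conclusion.** The point holds for all three M1 percentages in 10.4 B and for the attempted percentage alone in 10.3 and 11.1 B and C. As written, these denominators keep subjects with no M1 visit, and the manual-data line leaves room for two programmers to produce different M1 tables. The size depends wholly on how many subjects are lost after M0: under the assumptions above the ceiling lies anywhere from 79.7% to 100%, with 88.7% if the 12 losses divide equally.

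The consequence is limited to descriptive secondary tables. The primary test with its alpha and power, the 10.4 A rate, the success rate in the M1-ITT population (which already requires a complete M1 test) and the underestimation rate are unaffected. It is still more than a missing detail, because a stated rule mixes attrition with applicability in a secondary endpoint shown by visit.

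**What to change.** - In 10.4 B, for all three percentages, and in 10.3, 11.1 B and 11.1 C, for the attempted percentage, define the denominator at each visit as the EP subjects with the relevant lead (either lead for common vectors) who attended that visit.
- State that the manual-data restriction applies to tests at that visit.
- Show N at M0 and at M1, and footnote the number of EP subjects without the visit.
- Leave 10.4 A and the test-based percentages as they are.

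**Cost.** SAP wording and one derived flag for visit performed; no new data. The M0 and M1 denominators will differ, so a comparison between visits is no longer on one fixed set of subjects, which is why both N must be printed.
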